3.3. Approach

3.3.1. Research Design. This research design is illustrated in Fig 5. Aim 1 will use a cross-sectional design to determine baseline relationships between AGE level, intrinsic foot muscle volume, ankle joint mobility, MTPJ movement patterns and MTPJ extension alignment at baseline. Aim 2 is a clinical study with the foot specific intervention focused on improving foot and ankle strength, mobility, and function. The control group will receive a meaningful, comparable, but distinct intervention targeted at improving shoulder mobility, a common limitation in those with DMPN. All participants will repeat testing at 6 months, 1.5 years, and 3 years. Aim 3 will determine the key variables that predict progression of MTPJ extension deformity at 1.5 and 3 years. Intervention status will be entered as a potential predictor variable to examine the ability of a foot specific intervention to impact deformity progression.

Sixty-two participants with DMPN (defined below) and a wide range of MTPJ extension angle will be recruited and followed for 3 years. We will recruit a wide range of MTPJ extension angles to have broad variance in the magnitude and presentation of this deformity so we can understand better the primary factors with which it is associated. We will not break participants into groups based on amount/severity of MTPJ hyperextension allowing us to maintain the continuous nature of important predictors and dependent variables, and hence, increase power of our repeated measures research design.^{55, 56} Only participants with DMPN will

Figure 5: Research Design

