Aim 3: There is little existing evidence documenting the progression of diabetic foot deformity and we acknowledge that our work proposed in aim 3 is novel and exploratory. Aim 3 Ho3 is powered based on anticipated mean progression of MTPJ alignment 4° every 1.5 years after baseline in 50% people with DMPN assuming a standard deviation of 7.6° with a two-sided paired t-test. We assumed a much more conservative correlation of 0.6 between MTPJ alignment at baseline and 1.5 years later. Our preliminary data documented a progression in midfoot angle deterioration (Meary's angle) that worsened from -15.1 (14.3°) to -22.8 (14.2°) over 2 years in a group of subjects with a history of midfoot deformity, a correlation between measurement time points of 0.81.⁵⁸ Assuming a 20% attrition of the recruited sample, results in a required sample size of 62.

3.3.2. Subject recruitment will occur primarily from the Recruitment Enhancement Core of the Institute of Clinical And Translational Sciences here in the medical center. Several data bases are available to help recruit (e.g., Research Participant Registry through Volunteers for Health, and patient databases of the Applied Biomechanics and Human Biodynamics Laboratories). These resources have sufficient numbers of potential participants to help us achieve our goal. Potential participants will be mailed the consent prior to their first visit to allow them to carefully review the information and formulate questions regarding the study requirements. The requirements, risks and benefits of participation will be explained and all questions the potential participant may have will be answered. If willing to enroll in the study, written informed consent will be obtained. The potential participants will be screened and included if they meet the following inclusion and exclusion criteria:

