Aim 1: A multiple linear regression analysis will be used to test Aim 1. The primary dependent variable for Aim 1 will be baseline MTPJ alignment. The independent variables (predictors) for Aim 1 will be AGE level, intrinsic foot muscle volume, maximum ankle dorsiflexion, and MTPJ extension excursion during sit to stand. A Pearson correlation matrix will be obtained on all variables to understand better inter correlations. Adjusted R square from the multiple linear regression model will be obtained.

Aim 2: A repeated measures ANOVA analysis will be used to estimate the effect of the intervention by determining the between group changes over time in the primary outcome measures MTPJ extension alignment and the secondary outcome measures of intrinsic muscle volume, ankle joint dorsiflexion range of motion, MTPJ extension excursion during sit-to/from-stand and Foot and Ankle Ability Measure. Contrasts will be used to determine mean differences of interest.

Aim 3 Ho3: MTPJ deformity progression will be calculated as progression every 1.5 years (MTPJ deformity at baseline – MTPJ deformity at 1.5 years and MTPJ deformity at 1.5 years – MTPJ deformity at 3 years). Means and standard deviations for these differences will be obtained and paired t-tests will be performed to test for significant progression every 1.5 years. The proportion of individuals with DMPN and MTPJ deformity progression at 4 degrees or more within 1.5 years will be calculated with 95% confidence interval.

Aim 3 Ho4: MTPJ deformity progression will be assessed as progression at 1.5 and 3 years (MTPJ deformity at baseline – MTPJ deformity at 1.5 years and MTPJ deformity at baseline – MTPJ deformity at 3 years). Analysis of covariance model will be fitted to these two progression variables with intervention status as the major predictor adjusting for baseline measures of AGE level, intrinsic foot muscle volume, MTPJ extension excursion during sit to stand.

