All statistical tests will be two-sided with a significance level of 0.05 and performed with SAS 9.4. Careful attention will be paid to ensuring that data satisfy assumptions required of a particular analytic strategy. Thus, paired t-tests will only be accepted as valid if normality assumptions are satisfied. Similarly, we will evaluate regression residuals before we reach conclusions based on linear regression analysis. When required assumptions are violated, we will explore the use of data transformations and potentially, perform some analyses using non-parametric or semi-parametric methods based on the rank of some variables. In the event of multicollinearity with numerous predictors in regression models, highly redundant variables will be eliminated from the analyses, or where possible, composite variables will be formed to capitalize on the higher reliability of combined measures. Sample size limitations and potential multicollinearity may preclude the examination of all predictors in one analysis. To avoid this problem, we will examine the impact of predictors individually or in small, conceptually sensible, subsets.

3.3.7. Proposed Timeline and Plans for Future Studies.

We propose to complete the aims of this project in 5 years with the following milestones:

9/1/2015 – start date; Year 1: Methods and personnel are ready to begin testing immediately. Based on current recruitment methods, we are confident we can recruit and test 4 subjects per month. Therefore, we plan to conduct all baseline testing in the first 16 months of the study; 48 in year 1 and 14 in year 2. Data processing and entry into databases will occur on an on-going basis. Intervention will be initiated immediately after baseline testing has been completed

Year 2: Participant recruitment, baseline testing, intervention and 6 month follow up testing will be completed in year 2. Data analysis for baseline measures and the manuscript related to Aim 1 will be completed by the end of year 2. 1.5 year re-testing will begin on 24 subjects. Data analysis for Aim 2, 6 month data will be analyzed and the related manuscript prepared for publication.

Year 3: Complete 1.5 year re-testing on remaining 38 participants for total of 62 participants. Analyze and summarize all data.

Year 4: Complete 3 year retesting on 48 participants.

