Another potential limitation is that other factors besides those included in the specific aims may contribute to the development of acquired MTPJ deformities. For example, foot type^{1, 2}, other foot deformities (i.e., bunion), capsular or plantar plate tears at the MTPJ or plantar fascia that is torn or thickened^{28, 40} may reduce joint stability and allow the development of MTPJ deformity. For this reason, [name] will provide a clinical evaluation of all subjects to collect data on these variables and [name] will review all MR images for evidence of other substantial structural problems (i.e., plantar plate or plantar fascia tear) that may contribute to the deformity as described in sections 3.3.4.4.1 & 3.3.4.4.9.

In summary, the results of this study will have profound implications for helping to understand the causes and a corresponding treatment intervention for acquired neuropathic foot deformities. Understanding and treating the causes of acquired neuropathic foot deformities has great potential to halt or slow the cascade of events leading to amputation, while improving the mobility and minimizing disability in the 26 million people in the US with DM.

Protection of Human Subjects

Risks to Human Subjects

a. Human Subjects Involvement, Characteristics and Design

All methods for the proposed study titled “Muscle, joint and movement deterioration contributing to neuropathic forefoot deformity” have been approved by the Institutional Review Board and Human Research Protection Office (HRPO) of the Washington University School of Medicine and currently are being piloted. Review of the full proposal will occur prior to initiation of data collection or attainment of informed consent.

Subject groups. The proposed research will employ a single-group cross-sectional and longitudinal, repeated measures design composed of individuals with diabetes mellitus, peripheral neuropathy, and a wide range of metatarsalphalangeal joint hyperextension. Participants will be followed for 3 years with testing at baseline, 6 months, 1.5 years, and 3 years. The participants will be recruited primarily from St. Louis city and the surrounding metropolitan area. Age will be limited to less than ≤ 75 years to minimize extreme age related changes on muscle or joint.

Inclusion/exclusion criteria.

Inclusion Criteria (n=62)

- 1) Type 2 DM

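### Aim 3 Ho3 estimates deformity progression with no term for arm, so any benefit of the foot programme dilutes the estimate; progression should also be reported by arm

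*Combined protocol and SAP*

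**What the plan says.** Section 3.3.6 (Statistical Analyses), Aim 3 Ho3, forms two differences in MTPJ deformity, baseline to 1.5 years and 1.5 to 3 years. It states that "paired t-tests will be performed to test for significant progression every 1.5 years". It adds one proportion, with a 95% confidence interval, for participants who progress by at least 4° within 1.5 years. No arm term, stratum or restriction to one arm is given for either analysis.

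Section 3.3.1 (Research Design) randomises all participants after baseline to a foot or a shoulder programme. Section 3.3.5 (Intervention) gives limiting MTPJ deformity as the overall goal of the foot programme, says the shoulder programme was chosen so as not to affect foot and ankle outcomes, and continues home exercise for the rest of the 3 years.

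Arm does appear elsewhere. For Aim 3, section 3.3.1 says "Intervention status will be entered as a potential predictor variable to examine the ability of a foot specific intervention to impact deformity progression", and section 3.3.6 does this in the Ho4 ANCOVA, with progression from baseline to 1.5 and to 3 years as outcomes. Aim 2 has a repeated measures ANOVA of between-group change in MTPJ alignment, with contrasts that are not specified.

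The Ho3 sample size (section 3.3.1, repeated under Protection of Human Subjects) rests on "anticipated mean progression of MTPJ alignment 4° every 1.5 years after baseline in 50% people with DMPN". The calculation takes 7.6° as the SD, uses a paired t-test, sets the correlation at 0.6 and allows for 20% attrition from everyone recruited, giving 62.

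**The concern.** Ho3 is analysed as though the participants were one untreated cohort, whereas about half are assigned, throughout both intervals, to a programme aimed at the quantity being measured. If that programme has any benefit, the pooled mean lies between the two arms and describes neither, and so does the pooled 4° proportion.

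The sample size section says there is little existing evidence on how this deformity progresses, and section 3.3.7 expects the data to support future grants. A diluted figure could therefore be carried forward as the rate of progression in DMPN. The study's hypotheses also pull against each other: the better the foot programme works, the smaller the progression that Ho3 reports.

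**Working it through.** **Inputs from the documents**
- Test level: "All statistical tests will be two-sided with a significance level of 0.05" (section 3.3.6).
- SD of alignment 7.6°, correlation between time points 0.6, progression 4° per 1.5 years, attrition 20%, N = 62 (section 3.3.1, Aim 3).
- Equal arms: implied by 26 per group in the Aim 2 calculation; the randomisation ratio is not stated.

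**Assumptions**
- 80% power when reproducing the sample size (none is stated for Ho3).
- Control-arm progression of 4°, with 2° as a second case.
- The foot programme removes a fraction f of control progression; f is unknown and is varied from 0 to 1.
- Same SD of change in both arms.

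**1. Reproduce the plan's figure.** SD of change = 7.6 × √(2 × (1 − 0.6)) = 6.80°. A two-sided paired t-test for 4° at 80% power needs 25 pairs (noncentral t). Then 25 / 0.50 = 50, and 50 / 0.80 = 62.5, which matches the stated 62.

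**2. Completers.** 62 × 0.8 = 49.6, about 50 in all and 25 per arm.

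**3. Pooled mean.** With equal arms and control progression C, the pooled mean is ½C + ½C(1 − f) = C − ½(fC): control progression minus half the treatment effect. The SD of the pooled changes is √(6.80² + (fC/2)²).

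**4. Power by noncentral t, C = 4°**

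| f | Pooled mean | Pooled SD | Power, pooled (n = 50) | Power, controls only (n = 25) |
|---|---|---|---|---|
| 0 | 4.0° | 6.80° | 98% | 81% |
| 0.25 | 3.5° | 6.82° | 95% | 81% |
| 0.5 | 3.0° | 6.87° | 86% | 81% |
| 0.75 | 2.5° | 6.97° | 70% | 81% |
| 1 | 2.0° | 7.09° | 50% | 81% |

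Pooled power falls below controls-only power once f passes about 0.6.

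**5. Power if C = 2°** (for example, 4° in half of the participants and none in the rest, keeping the SD of change at 6.80°). Pooled: 53% at f = 0, 33% at f = 0.5, 17% at f = 1. Controls only: 29% throughout. The crossing point is again about f = 0.6.

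**6. Proportion progressing by 4° or more**, assuming normally distributed changes and C = 4°. Controls: 50%. Foot arm: 38% if its mean is 2°, 28% if its mean is 0°. Pooled: (50 + 38) / 2 = 44% at f = 0.5, and (50 + 28) / 2 = 39% at f = 1.

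**7. Precision.** The 95% half-width for a mean change is t × 6.80 / √n: 2.064 × 6.80 / √25 = 2.8° for one arm, and 2.010 × 6.80 / √50 = 1.9° pooled (taking f = 0).

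**The case against.** **Arm is already handled.** Aim 2 compares the arms over time with MTPJ alignment as primary outcome, and Ho4 makes intervention status the major predictor of progression. This stands in part. A reader might infer that a null Ho3 could not be told apart from an effective programme; the documents do not support that, because Ho3 would be read beside both analyses. What they leave open is narrower. Ho4 measures change from baseline only, so it does not give the 1.5-to-3-year interval as such. The Aim 2 contrasts are not specified, nor is it stated which visits enter that model. Neither is stated to give the 4° proportion by arm.

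**The estimand is assumed.** The available text does not say that Ho3 estimates untreated progression. As a test of whether the enrolled cohort changed on average, the paired t-test is valid, and pooling does not inflate its type I error. This stands, and is why the pooled test can remain. The dilution matters when the result is described as progression in DMPN without the foot programme.

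**Pooling is inferred.** The plan never says that the arms are combined. That is fair, but Ho3 has no arm term while the next paragraph, Ho4, names one, and the Ho3 sample size uses the whole sample. The description of the design as "single-group cross-sectional and longitudinal, repeated measures design" under Protection of Human Subjects adds little: it introduces one disease population, and the same section goes on to describe randomisation.

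**The dilution may be small, and a control-only test may lose power.** Both stand. Section 3.1.5 allows that neuropathic muscle may respond little to exercise, and contact with the therapist ends after 4 to 5 months. A reader might infer that a control-only test should replace the pooled one. The working does not support that as a general rule, since pooling is more powerful until the programme removes about 60% of progression.

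**Conclusion.** The point holds as a matter of estimation and reporting. As written, Ho3 gives an average over two randomised arms. With equal arms, that average understates progression without the foot programme by half the treatment effect: 1° if 4° of progression is halved, 2° if it is abolished, nothing if the programme has no effect. The 4° proportion is diluted in the same direction, from 50% to 44% or 39% in those two cases.

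The half-effect rule needs only equal arms. The degree and power figures also rest on the plan's SD and correlation, about 50 completers and an assumed 4° in controls; the proportions additionally assume normality. The size of the programme's effect is unknown, so these are illustrations and not forecasts. The point does not invalidate the Ho3 test or Aim 3, which the plan itself calls exploratory.

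**What to change.** In section 3.3.6, Aim 3 Ho3:

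- State that the paired t-tests combine both arms. Keep them as the cohort-level test, and describe the pooled mean and proportion as averages over the two arms.
- Add the mean change for 0 to 1.5 and 1.5 to 3 years by arm, with 95% confidence intervals. These can come from the Aim 2 model if it is stated to include all visits, with arm-by-visit contrasts for the two intervals.
- Add the proportion progressing by 4° or more by arm, with 95% confidence intervals.
- Use the shoulder-arm estimate wherever progression in DMPN without the foot programme is described.

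This needs no new data, visits or participants. It costs some wording, one more table and the wider per-arm intervals shown in the working.

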be recruited (vs. otherwise healthy people with MTPJ deformity) so we can focus on the muscle and limited joint mobility problems unique to DMPN. Measures will be taken at baseline, as described below in Table 1, and then all participants will be randomized into a foot specific or a shoulder specific intervention group. Participants will receive 6 intervention visits and a home program. Physical therapist directed interventions will occur during the first 4 months of study participation (3 visits in the first month, and then 1 per month for 3 months). Participants will be instructed, and encouraged by phone call follow up, to continue the home program for the duration of study enrollment. The research coordinator will call participants every 3 months to determine any change in medical status (i.e., skin breakdown, medical emergency), assess adherence with the home program and to keep them “connected” to the study. Participant testing will be repeated at 6 months, 1.5 years, and 3.0 years so that impact of treatment and predictors of change in deformity can be examined. Although we consider this clinical study preliminary, testers will be blinded to group assignment, treatments will take place in a different location than the assessments, and CONSORT guidelines will be followed.

Sample size determination.

Aim 1: A power analysis was conducted based on Hsieh et al's⁵⁷ sample size calculation for logistic and linear regression. 62 participants with DMPN are needed to detect a significant correlation of .44 between the predictor (intrinsic foot muscle volume) and the dependent variable (baseline MTPJ alignment) after adjusting for the other variables (AGE level, maximum ankle dorsiflexion, and maximum MTP extension during ankle dorsiflexion tasks), assuming all the predictors account for 37% of baseline MTPJ alignment. We are confident we will achieve these values for aim 1 since our preliminary data showed a higher correlation ($r=0.60$).

Aim 2: The power analysis for the pilot clinical study is based on a two-sample t-test. We anticipate an effect size of mean ankle joint dorsiflexion range of motion at 6 months, between the foot and shoulder specific intervention groups, of $4 \pm 5^\circ$.⁴⁶ A sample of 52 (26 in each group) will be able to detect this effect size. Our targeted sample size 62 is conservative for this aim considering very low attrition rate at 6 month.

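### The Ho4 ANCOVA of change in MTPJ alignment leaves out baseline MTPJ alignment: precision only is lost for the randomised effect, by an amount between nothing and about 10% of the standard error

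*Combined protocol and SAP*

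**What the plan says.** Section 3.3.6, Aim 3 Ho4, defines two outcomes, both changes from baseline in MTPJ deformity: to 1.5 years and to 3 years. Each is fitted by analysis of covariance with intervention status as the main term, "adjusting for baseline measures of AGE level, intrinsic foot muscle volume, MTPJ extension excursion during sit to stand". Neither this paragraph nor any other adds baseline MTPJ alignment. The closing paragraph of 3.3.6 only allows predictors to be removed, combined or examined in subsets.

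Section 3.3.1 gives Ho4 two purposes. One is prediction: "Aim 3 will determine the key variables that predict progression of MTPJ extension deformity at 1.5 and 3 years". The other is the randomised comparison: "Intervention status will be entered as a potential predictor variable to examine the ability of a foot specific intervention to impact deformity progression".

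Baseline alignment is available. Section 3.3.4.2 makes the resting MTPJ angle on CT the primary outcome measure, Table 1 schedules CT at baseline, and on timing section 3.3.1 says: "Measures will be taken at baseline, as described below in Table 1, and then all participants will be randomized".

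The sample size text for Aim 3 supplies the correlations. The planning value is "We assumed a much more conservative correlation of 0.6 between MTPJ alignment at baseline and 1.5 years later"; the preliminary value, for a midfoot angle over 2 years, is "a correlation between measurement time points of 0.81". The same paragraph says that "our work proposed in aim 3 is novel and exploratory".

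**The concern.** A change score fixes the slope of follow-up on baseline at 1. With equal SDs at the two visits, the plan's correlation of 0.6 implies a slope of 0.6. The part of baseline alignment that the fixed slope handles wrongly stays in the residual, unless the three listed covariates happen to absorb it. Putting baseline alignment in the model lets the data estimate the slope.

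What is at stake is the precision of the randomised intervention effect on progression, estimated from about 50 people, when the measurement that would sharpen it is already in the dataset.

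**Working it through.** **Inputs.** Recruited sample 62 with 20% attrition (Aim 3 sizing): 62 × 0.8 = 49.6, taken as n = 50, split 25 and 25. SD 7.6°. Correlation ρ = 0.6 (planning) or 0.81 (preliminary midfoot data). Two-sided alpha 0.05. The share R² of baseline alignment explained by the other covariates runs from 0 to 0.37. The upper value comes from the Aim 1 sizing, "assuming all the predictors account for 37% of baseline MTPJ alignment", which refers to four predictors; Ho4 has three, so 0.37 is used as an upper value.

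**The plan's own figure first.** Read 7.6° as the SD at one visit. The SD of change is 7.6 × √(2 × (1 − 0.6)) = 6.80°. A two-sided paired t-test for 4° at 80% power (assumed; the plan states none) needs 25. Dividing by 0.5 for progression in half of people gives 50, and 50/0.8 = 62.5 against the stated 62. Reading 7.6° as the SD of change needs 31, and 31/0.5/0.8 = 77.5, which does not fit. So 7.6° is used as a per-visit SD. Ho4 has no sizing of its own.

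**Residual variance.** Assume equal SDs at both visits, and covariates related to follow-up only through baseline alignment. In units of the per-visit variance:

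- without baseline: (1 − ρ)²(1 − R²) + (1 − ρ²)
- with baseline: 1 − ρ²

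At ρ = 0.6 and R² = 0 this is 0.16 + 0.64 = 0.80, falling to 0.64. At R² = 0.37 it is 0.16 × 0.63 + 0.64 = 0.741, falling to 0.64.

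**Standard error of the intervention effect.** SE = 7.6 × √(variance × 4/50 × 47/(47 − k)), with k = 3 covariates without baseline and 4 with it. The last factor is the expected cost of chance imbalance, so the extra degree of freedom is paid for. Example: 7.6 × √(0.80 × 0.08 × 47/44) = 1.99° and 7.6 × √(0.64 × 0.08 × 47/43) = 1.80°.

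| ρ | Variance without (R² 0 / 0.37) | Variance with | SE without | SE with | SE smaller by |
|---|---|---|---|---|---|
| 0.6 | 0.800 / 0.741 | 0.640 | 1.99° / 1.91° | 1.80° | 9.5% / 6.0% |
| 0.81 | 0.380 / 0.367 | 0.344 | 1.37° / 1.35° | 1.32° | 3.8% / 2.0% |
| 0.9 | 0.200 / 0.196 | 0.190 | 0.99° / 0.98° | 0.98° | 1.4% / 0.5% |

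The plan gives no 3-year correlation. If it were 0.5 (assumption), the SE would be 8-12% smaller.

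**Effect of recruiting in thirds.** Section 3.3.2 recruits one third of participants below 30°, one third at 30-50° and one third above 50°. On a normal curve centred at 40° this needs an SD of 10/0.431 = 23.2°. If the SD of change stays at 6.80° (assumption), ρ = 1 − 6.80²/(2 × SD²):

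| Baseline SD | ρ | Change in SE (R² 0 / 0.37) |
|---|---|---|
| 12° | 0.84 | 3.0% / 1.5% smaller |
| 15° | 0.90 | 1.5% / 0.5% smaller |
| about 23° | 0.96 | 0.1% / 0.5% larger |

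**Power.** The plan gives no Ho4 effect size, so two illustrative arm differences are used with the noncentral t distribution (SD 7.6°).

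- 4°: from 50-54% to 59% at ρ = 0.6, and from 82-83% to 84% at 0.81.
- 2°: from 17-18% to 19% at 0.6, and from 30-31% to 32% at 0.81. Mean progression is 2° if half of people progress by 4° and the rest not at all (assumption).

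**Validity.** In simulations of 20,000 trials per setting at n = 50, the mean estimate was 3.99-4.01° for a true 4°, and rejection under no effect was 4.5-5.2%, with and without baseline. The simulated cuts in SE were 9.2% / 6.0% at 0.6 and 3.7% / 2.1% at 0.81, in line with the formula.

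**The other predictors.** A separate simulation (8,000 trials, assumed covariate correlations, R² = 0.37) gave muscle volume no effect once baseline alignment is known. The model without baseline still flagged it in 22% of trials at ρ = 0.6 and 12% at 0.81, against about 5% with baseline. The two models ask different questions of these non-randomised predictors.

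**The case against.** **The gain may be close to nil.** The value 0.6 is a cautious sizing assumption, and the only observed correlation is 0.81. Recruitment in thirds cannot fit an SD of 7.6°: even with all participants placed at 30°, 40° and 50°, the SD is √(200/3) = 8.2°. A wider spread with the same SD of change pushes the correlation up and the gain towards zero. This stands and sets the lower end of the range. It is softened because screening uses a goniometer and the outcome uses CT, so the two spreads need not match, and because the worst loss is about 0.5% of the SE.

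**The 4° power figure flatters.** The sizing text expects 4° in only half of people. If the others do not progress, a 4° arm difference exceeds complete prevention of the 2° average. This stands, so the 2° figures belong beside it.

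**The change is not free for the predictor question.** Sections 3.1.2 and 3.1.4 put forward AGE level and the movement pattern, among others, as predictors under Ho4, and muscle volume correlates 0.60 with baseline angle in the preliminary data (3.3.4.3). Adding baseline alignment changes what these coefficients mean. This stands and makes reporting both versions a requirement.

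**Aim 2 already tests the intervention on MTPJ alignment.** True, and Ho4 is exploratory. That limits the consequence, but Aim 2 does not fill the gap in the Ho4 model.

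A reader might also infer that the Ho4 intervention test is biased or has the wrong error rate. It does not: allocation is random and follows the baseline measurements, so both models estimate the same effect.

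**Conclusion.** The omission is certain; the size of the benefit is not. For the randomised effect, adding baseline alignment makes the SE 6-10% smaller at the plan's correlation of 0.6 and 2-4% smaller at 0.81. There is no gain, and at worst a 0.5% larger SE, at about 0.96. The last case needs a baseline SD near 23° and an SD of change that stays at 6.8°. All figures assume 50 completers in equal arms, equal SDs at the visits, and covariates that explain 0-37% of baseline alignment and relate to follow-up only through it.

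It would be too strong to present this as an assured gain of up to 10%, or as a rise in power from about 50% to 59% that the trial can count on. The documents give no Ho4 effect size and no observed MTPJ correlation over time. This is a modest improvement worth making because it costs so little, and no conclusion of the trial is shown to depend on it.

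**What to change.** In section 3.3.6, Aim 3 Ho4:

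1. Prespecify baseline MTPJ alignment (resting CT angle) as a covariate in both models, 1.5 and 3 years, for the estimate of the intervention effect.
2. State that it stays in the model if the multicollinearity rule at the end of 3.3.6 is applied to the other predictors. Its correlation with muscle volume could otherwise lead to its removal.
3. Require the AGE level, muscle volume and excursion coefficients to be reported twice: without baseline alignment, labelled as predicting change, and with it, labelled as predicting later alignment given the starting angle.

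The cost is a few lines of text, one degree of freedom and one extra set of coefficients. No new data or visits are needed, and no change to Aim 2 is proposed.
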